## 2 RATIONALE

### 2.1 Study Rationale and Purpose

The glycoprotein spikes on the surface of SARS-CoV-2 utilize membrane ACE2 receptors and TMPRSS2, to enter the host cells (6). Thus, targeting the expression or activity of ACE2 or TMPRSS2 plays a critical role in reducing the pathogenicity of coronavirus infection, GT0918 can down-regulate the ACE2 and TMPRSS2 expression in prostate, lung cancer cell lines and lung epithelial cell lines. Furthermore, the clinical study of GT0918 in Brazil for COVID-19 (NCT04446429) showed a clinically meaningful SARS-CoV-2 viral load reduction and clearance, decreased the hospitalization rate significantly in the GT0918 group compared to the placebo group. Therefore, GT0918 may be an efficient option to improve clinical outcome and reduce the rate of hospitalization in COVID-19 infected patients. Since SARS-CoV-2 replication is greatest just before or soon after symptom onset, GT0918 is likely to be most effective when used early. Therefore, in this study, GT0918 will be administered to evaluate the efficacy and safety in COVID-19 infected outpatients with mild or moderate symptoms.

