##### 7.1.1.3 Subject Demographics and Other Baseline Characteristics

The data that will be collected at screening includes:

- Demography (date of birth and initials (where permitted), sex, race, ethnicity), BMI.
- Diagnosis (date and method of confirmation the positive SARS-CoV-2 test result).
- Days from onset of COVID-19 symptoms prior to first dosing.
- Medical History(including medication allergy history)/current medical conditions (e.g., all current medical conditions which are present at the time of signing informed consent). High-risk status for severe COVID-19 illness (such as hypertension, diabetes, coronary artery disease, obesity, chronic kidney disease, smoker, androgenic alopecia etc.). Ongoing medical conditions, symptoms and disease which are recorded on the medical history eCRF should include the toxicity grade.
- All medications and significant non-drug therapies taken within 30 days before the first dose is administered, they must be recorded on the Prior and Concomitant medication or Surgical and medical procedures eCRF page and updated on a continual basis if there are any new changes to the medications.
- Patient reported symptom questionnaires.
- Counsel subjects to use adequate birth control methods required during the study to avoid pregnancy.
- Obtain vital signs (including as below)

- Height and weight are only needed at screening
- Body temperature.
- Systolic blood pressure (BP), diastolic BP.
- Pulse rate.
- Respiration rate.
- Saturation of peripheral oxygen if applicable.
- Supplemental oxygen flow rate, FiO2 if known, and method of delivery, if applicable or clinical indicated.
- Additional vital signs may be measured during the study if warranted, as determined by the investigator.
- Review recent radiographic imaging (X-ray or CT-scan) if applicable
- A complete physical examination will be performed at the screening visit.
  - This examination excludes pelvic, rectal, and breast examinations unless clinically indicated.
  - A symptom directed physical examination will be performed at other visits, as specified in the SoA and as clinically indicated.
  - Investigators should pay special attention to clinical signs related to COVID-19, to ongoing medical conditions and to previous serious illnesses.
- Obtain blood for screening laboratory evaluations.
- Serum pregnancy test (regardless of childbearing potential).

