#### **10.5.2.4 Time to symptom resolution**

Time to all symptom resolution is defined (in days) as:

*First study day when symptom resolution status is changed to "Yes" – first dosing Date + 1.*

If a patient has not experienced symptom resolution by completion or early discontinuation of study/study treatment, the patient will be censored at the date of their last visit during the treatment period.

Time to symptom resolution will be evaluated up to Day 28 and will be summarized by treatment and listed. Cox proportional hazard model will be used, stratified by duration since symptom onset to randomization category.

Time to symptom resolution will be presented graphically.

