4.10.3 Secondary Efficacy Variables

Hospitalization Percentage

Hospitalization percentage is defined as the percentage of subjects who experience any of the following events due to all causes by Day 28:

- Hospitalization for \geq 24 hours or
- Supplemental oxygen for \geq 24 hours in response to $\text{SpO}_2 \leq 93\%$ or
- Death

The same process used for the primary endpoint analysis will be used to compare the difference between treatment groups.

The following sensitivity analysis for hospitalization percentage will be performed among subset of mITT subjects:

- With dosing days > 7 days;
- With one or several major risk factors below:
 - Single risk factor: age (≥ 50 years; ≥ 60 years), major underlying medical conditions (overweight, obesity, hypertension, diabetes, smoking);
 - Combination of age factor in column 1 and other major underlying medical conditions in column 2 in the table below (e.g., age ≥ 50 years and/or obesity at randomization; age ≥ 60 years and/or obesity at randomization);

Age	Major underlying medical conditions
≥ 50 years	Overweight
≥ 60 years	Obesity Hypertension Diabetes Smoking

- With aged ≥ 50 years and days from symptom onset to study randomization ≤ 5 days and days from the positive SARS-CoV-2 Prior to first dosing ≤ 3 days;
- With aged ≥ 50 years and higher than normal biomarkers (CRP, Ferritin, D-dimer).

All sensitivity analyses will be conducted using one-sided CMH chi-square tests used for the primary endpoint analysis. Forest plots for the sensitivity analysis will be presented.

Change from Baseline to Days 3, 7, 14 and 28 in SARS CoV-2 Viral Load

Change of SARS-CoV-2 viral load from baseline, which will be evaluated in log base 10 scale, will be summarized, and plotted by treatment group and listed. Two sample t-tests will be used to compare differences in the change of SARS-CoV-2 viral load between treatment groups at Day 3, 7, 14 and 28, respectively.

Also, an analysis of covariance (ANCOVA) model will be used to compare the change from baseline in SARS-CoV-2 viral load at Day 3 with fixed effects for treatment group, age and stratification factors (sex, race and ethnicity, and number of risk factors), and baseline viral load as a covariate. If systematic pattern is identified from the residual of predicted values, a transformation of the baseline viral load will be employed to improve the performance of the model. Estimated treatment differences

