
All hospitalization events and COVID-19 related medical attended visits will be listed.

Time to Hospitalization

Time to Hospitalization (in days) is defined as:

First hospital admission date - first dosing date + 1.

Note: Hospitalization (≥ 24 hours) includes Hospitalization, Emergency room and ICU. Extended Care Facility Admittance is excluded.

The following two summaries will be generated separately:

- All-Cause Hospitalization
- COVID-19 Related Hospitalization

If a patient has not experienced hospitalization by completion or early discontinuation of study/study treatment, the patient will be censored at the date of their last visit during the post-treatment period.

Time to hospitalization will be evaluated up to Day 28 and will be summarized and plotted by treatment group with mITT set using the Kaplan-Meier (KM) method. The 2-sided 95% CIs for the 25th, 50th and 75th percentiles, as well as at days 3, 7, 14 and 28 using the Brookmeyer and Crowley method will be reported when estimable. P-value will be obtained from the log-rank test stratified by age, and sex, race and ethnicity, and number of risk factors at randomization. Hazard ratios and corresponding 95% confidence intervals will be obtained from a Cox proportional hazard model which treated treatment group as a unique covariate, and age, and sex, race and ethnicity, and number of risk factors as stratas. The Cox proportional hazard model will be also performed by subgroup of duration since symptom onset to randomization category (≤ 3 days; > 3 days).

If cases of hospitalization are too sparse (e.g., < 1 case in one treatment group), no time to hospitalization analyses will be performed.

Proportion of Symptom Resolution

All symptom resolution is defined as

all symptoms (those scored 0-3*) on the symptom questionnaire scored as absent (scored 0), with each symptom resolution absent for at least 48 hours.

Note: * Seven individual questions from COVID-19-Related Symptom Questionnaire are included here: questions 3, 4, 5, 6, 7, 8 and 9.

Additionally, all symptom resolution will be defined differently to include all individual questions scored 0-3 and related outputs will be noted as sensitivity analysis. It is defined as

all symptoms (those scored 0-3*) on the symptom questionnaire scored as absent (scored 0), with each symptom resolution absent for at least 48 hours.

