First date when all symptom resolution status is changed to 'Yes' - first dosing date + 1.

If a patient has not experienced symptom resolution by completion or early discontinuation of study/study treatment, the patient will be censored at the date of their last visit during the post-treatment period.

Time to all symptom resolution will be applying the same KM methods and Cox proportional hazard models introduced in the time to hospitalization section.

Symptom Improvement

Symptom improvement is defined as a change in severity of overall symptoms * from a higher score to a lower score, which is defined as following:

symptoms scored as moderate or severe at baseline are scored as mild or absent,
OR

symptoms scored as mild or absent at baseline are scored as absent.

Note: * The overall symptoms question (overall question 1) under overall COVID-19 related symptoms from COVID-19-Related Symptom Questionnaire is included here.

Additionally, symptom improvement will be defined by individual symptom questions from symptom questionnaire as below and related outputs will be noted as sensitivity analysis. It is defined as a patient experiencing both:

symptoms * scored as moderate or severe at baseline are subsequently scored as mild or absent,

AND

symptoms * scored as mild or absent at baseline are subsequently scored as absent.

Note: * Seven individual questions from COVID-19-Related Symptom Questionnaire are included here: questions 3, 4, 5, 6, 7, 8 and 9.

The proportion of subjects with symptom improvement at Days 3, 7, 11, 14 and 28 will be summarized by treatment in frequency tables and listed using mITT set. Generalized estimating equation (GEE) model is fitted with the response of symptom improvement mapped to categories of Yes or No and with treatment, age, stratification factors (sex, race and ethnicity, and number of risk factors), time effect and time*treatment interaction terms included in the model as covariates. Odds ratios with 95% confidence intervals and p-values will be present.

Time to Symptom Improvement

Time to symptom improvement (in days) is defined as:

Date when symptom improvement status is changed to 'Yes' - first dosing date + 1.

If a patient has not experienced symptom improvement by completion or early discontinuation of study/study treatment, the patient will be censored at the date of their last visit during the post-treatment period.

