Time to TEAEs of special interest will be summarized for Safety set using the Kaplan-Meier (KM) method. Log-rank test will be used. P-values and hazard ratios with 95% confidence intervals based on Cox proportional hazard model stratified by duration since symptom onset to randomization category (≤ 3 days; > 3 days) will be present.

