5 REFERENCES

- [1] SAS® Version 9.4 of the SAS System for Personal Computers. Copyright © 2002-2003. SAS Institute Inc. SAS and all other SAS Institute Inc. product or service names are registered trademarks or trademarks of SAS Institute Inc., Cary, NC, USA.
- [2] Division of AIDS (DAIDS) Table for Grading the Severity of Adult and Pediatric DAIDS Adverse Event Grading Tables | DAIDS Regulatory Support Center (RSC) (nih.gov)

6 APPENDICES**6.1 Schedule of Assessments (SoA)**

Table 4 Schedule of Activities

-	Screen	Treatment Period					Early Withdrawal ¹⁹	Post-treatment		Safety Follow Up ²⁰
Study Day (Visit Window ± days)	D-1	D1	D3	D7 (±1)	D14 (+1)		(+2)	D15	D28 (±2)	D42 Phone Call (±2)
Informed Consent	X									
Inclusion/Exclusion Review¹	X									
Demographics²	X									
Preexisting Conditions and Medical History³	X									
NIAID Ordinal Scale⁴	X	Daily								
Prior Treatment⁵	X									
Tobacco Use	X									
Physical Examination⁶	X	Symptom Directed PE only if Clinical Indicated								
Vital Signs⁷	X		X	X	X	X			X	
Nasopharyngeal swabs⁸	X		X	X	X	X			X	
Randomization⁹	X	X								
Hematology¹⁰	X			X	X	X			X	
Chemistry¹⁰	X			X	X	X			X	
Biomarkers¹⁰	X		X		X	X			X	
Coagulation¹⁰	X				X	X			X	

Drugs and Diary Dispense¹¹	X	X							
GT0918 or Placebo Administration¹¹			Daily from D1 to D14						
Subject Diary¹¹	X		Daily from D1 to D14						
Questionnaire (Symptoms; Overall Clinical Status;)¹¹					Daily				
Chest X-ray or CT Scan¹²					Clinically Indicated				
12-ECG¹²					Clinically Indicated				
Hospitalization events¹³						Daily			
Clinical status and concomitant procedures if subject is hospitalized¹⁴						Daily if hospitalized			
Adverse Events¹⁵							X		
Concomitant Medications¹⁶							X		
Pharmacokinetics¹⁷		X	X	X	X				
Pregnancy test¹⁸	X							X	
COVID-19 vaccination status	X								

Annotation:

1. Inclusion/Exclusion review: every subject needs to meet all inclusion and exclusion criteria. The eligibility checklist needs to be signed by the investigator or sub-investigator.
2. Demographics: includes age, gender, race, and ethnicity.
3. Pre-existing conditions and medical history: obtained from interview or available information and including timing of exposure and onset of symptoms suggestive of SARS-CoV-2 infection.

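### For time to symptom resolution the SAP replaces the protocol's symptom-duration stratum without giving a reason, so no overall efficacy estimate is adjusted for this baseline value, which is already collected

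*SAP*

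**What the plan says.** **Collection.** Protocol 7.1.1.3 lists "Days from onset of COVID-19 symptoms prior to first dosing" among the screening data. The SAP schedule (6.1, annotation 3) takes medical history "including timing of exposure and onset of symptoms suggestive of SARS-CoV-2 infection".

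**Protocol model.** For time to symptom resolution, protocol 10.5.2.4 states: "Cox proportional hazard model will be used, stratified by duration since symptom onset to randomization category". No other protocol efficacy model has a duration term.

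**SAP model.** SAP 4.10.3 states: "Time to all symptom resolution will be applying the same KM methods and Cox proportional hazard models introduced in the time to hospitalization section". The Cox model in that section is one "which treated treatment group as a unique covariate, and age, and sex, race and ethnicity, and number of risk factors as stratas", and its log-rank test uses the same strata. The viral-load ANCOVA has "fixed effects for treatment group, age and stratification factors (sex, race and ethnicity, and number of risk factors), and baseline viral load as a covariate". The viral and symptom MMRM and GEE models follow the same pattern, with baseline viral load or baseline symptom score in the MMRMs and no duration term.

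**Where duration remains in the SAP.**
- Additional Cox fits within the subgroups of at most 3 days and more than 3 days (4.10.3).
- A descriptive primary-endpoint subgroup split at 5 days (4.10.1.3).
- Part of the definition of one sensitivity subset for hospitalization percentage (4.10.3).
- The baseline summary (4.6).
- The safety model for time to adverse events of special interest, which is "stratified by duration since symptom onset to randomization category" (4.11.3).

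**The concern.** The protocol named one efficacy model in which stage of illness at entry would be controlled. The SAP removed it there and kept the same stratum in a safety model. Protocol 10.1 lets the SAP prevail where the two differ, so the change takes effect. No reason is recorded: the revision history says only that detail was added to the time-to-event analysis, and section 4.10.1.1.3, which explains departures from the protocol, deals with missing data.

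The protocol gives grounds for expecting duration to matter. Section 2.1 begins its case for early treatment with "Since SARS-CoV-2 replication is greatest just before or soon after symptom onset". Randomization is not stratified by duration, so chance imbalance in illness stage is not controlled by design.

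The subgroup Cox fits do not fill the gap. They give two hazard ratios, each from part of the sample, and no adjusted overall estimate or p-value. At stake are precision on the symptom and viral secondary endpoints and protection against chance imbalance.

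**Working it through.** **1. The plan's own figure.** The only stated power is for the primary endpoint: 97% versus 91%, 668 subjects, one-sided 0.025, about 90%. The two-proportion formula gives 328 per arm (656) without an interim look. At 334 per arm with an O'Brien-Fleming-type look at half the information, power is 90.3% to 90.8%. The figure reproduces. The documents state no power for any symptom or viral endpoint, so everything below rests on assumptions.

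**2. Number of cells.** The SAP strata are sex (2) × race/ethnicity (3) × risk factors (3) × age. With age in two groups (an assumption) that is 2 × 3 × 3 × 2 = 36 cells, about 668/36 = 18.6 subjects each. Adding a two-level duration stratum makes 72 cells, about 668/72 = 9.3 each.

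**3. Time to symptom resolution, log-rank.** From the documents: 668 subjects, 1:1, evaluated to Day 28. Assumed: treatment hazard ratio 1.25, median 10 days, half the subjects in each duration category, age in two groups, two-sided 0.05. Simulated power in percent, 3,000 trials per setting, Monte Carlo error about 1 point:

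| Duration hazard ratio | 1.0 | 1.25 | 1.5 | 2 | 3 |
|---|---|---|---|---|---|
| SAP strata (36 cells) | 72 | 73 | 70 | 64 | 55 |
| Duration in place of age (36 cells) | 72 | 73 | 72 | 72 | 70 |
| Duration added to SAP strata (72 cells) | 67 | 67 | 66 | 67 | 64 |
| Gain, in place of age | 0 | 0 | +2 | +8 | +15 |
| Gain, added stratum | −5 | −6 | −4 | +3 | +9 |

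**4. Duration as a Cox covariate.** Same treatment hazard ratio and median, 600 trials per setting, error about 2 points, duration hazard ratio 1 / 1.5 / 2 / 3:
- SAP strata alone: 69 / 68 / 62 / 53%
- SAP strata plus duration covariate: 69 / 69 / 68 / 67%
- Gain: 0 / 1 / 6 / 14 points

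A second set of assumptions (treatment hazard ratio 1.30, median 12 days, 1,500 trials; duration hazard ratio 1.0 / 1.3 / 1.6 / 2.0) gives 81 / 81 / 80 / 73% with SAP strata and 81 / 82 / 81 / 80% with the covariate, a gain of 0 / 1 / 1 / 7 points.

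**5. Age grouping.** The SAP gives no age categories for these strata. Under the second set of assumptions, if age were used in single years (assumed mean 45, SD 14), power would fall to 25% to 32%, because most cells would hold too few subjects to contribute. The stratum wording needs attention in any case.

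**6. Linear contrasts (ANCOVA, MMRM).** If days since onset explains a further partial R-squared of R², the standard error is multiplied by √(1 − R²), and the equivalent sample is 668/(1 − R²).

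| R² | Interval shorter by | Extra subjects, equivalent | 80% power becomes |
|---|---|---|---|
| 2% | 1 − √0.98 = 1.0% | 668/0.98 − 668 ≈ 14 | 80.8% |
| 5% | 1 − √0.95 = 2.5% | 668/0.95 − 668 ≈ 35 | 82.0% |
| 10% | 1 − √0.90 = 5.1% | 668/0.90 − 668 ≈ 74 | 84.0% |

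**The case against.** The strongest reply is that the SAP prevails by the protocol's own rule, that stratifying by the randomization factors plus age is conventional, and that no document shows duration to be strongly prognostic. Protocol 2.1 argues about when treatment is likely to work, which the subgroup Cox fits address. It does not establish prognostic value beyond the covariates already in the models. Entry is limited to 5 days from onset, which narrows the range, and the viral-load ANCOVA and MMRM and the symptom-score MMRM already adjust for the baseline value of the outcome. All of this stands. It limits the likely gain, but it does not explain why the stratum was removed.

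Several stronger readings are tempting and are not supported:

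- **That no efficacy analysis uses duration.** The SAP has the subgroup Cox fits and a sensitivity subset. What is missing is duration as a covariate or stratum in an overall estimate.
- **That a commitment was dropped for viral endpoints or symptom improvement.** Protocol 10.5.2.8 plans only summaries and a plot for time to clearance, 10.5.2.9 a mixed model with no onset term, and 10.5.2.6 summaries and a Kaplan-Meier plot. One endpoint changed.
- **That the loss is the gap between an unstratified and a duration-stratified test.** The SAP's test is not unstratified, so its own strata are the right comparator.
- **That leaving duration out biases the hazard and odds ratios.** In a randomized trial much of the shift toward 1 is non-collapsibility: the less-adjusted ratio is a valid but different target.
- **That omitting vaccination status is a defect.** Both documents plan it only as an exploratory subgroup, and nothing in them gives its prevalence or effect.

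**Conclusion.** The point holds for one endpoint as an unexplained departure from the protocol, and for the other symptom and viral endpoints as a modest missed gain in precision. For time to symptom resolution, against the SAP's own strata, the gain is about 0 to 2 power points for a duration hazard ratio up to 1.5 and about 5 to 15 points at 2 to 3. For linear contrasts, intervals shorten by about 1% to 5% at partial R-squared 2% to 10%. These sizes depend on the assumed treatment effect, median, category split and age grouping, and above all on a prognostic strength that the documents do not give. The case for acting is that a duration covariate cost no power in these simulations when duration was uninformative, and it helps if duration is strong. That does not extend to adding duration as a further stratum, which loses about 4 to 6 points up to a hazard ratio of 1.5. These are secondary endpoints; the primary analysis and its sample size are unaffected.

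**What to change.** 1. In SAP 4.10.3, give time to symptom resolution its own model statement instead of the cross-reference to the hospitalization section. Include duration since onset (at most 3 days; more than 3 days, the categories the SAP already uses) either as a Cox covariate or as a stratum in place of age in both the Cox and log-rank analyses. Do not add it on top of the existing cells. With the covariate option, state which p-value is the main one, because the separate log-rank p-value would remain unadjusted for duration. If the protocol's stratum is deliberately left out, record the reason.
2. State the grouping of age wherever it remains a stratum.
3. Add days since onset as a covariate in the other symptom and viral time-to-event, ANCOVA, MMRM and GEE models. Vaccination status is an optional further covariate.
4. Leave the hospitalization models as they are; events there may be too sparse to support more terms.

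The cost is SAP wording and about one degree of freedom per model for days since onset, using data already collected. The change should be fixed before unblinding.

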6.2 NIAID 8-Point Ordinal Scale

- 1 Death
- 2 Hospitalized, on invasive mechanical ventilation or extracorporeal membrane oxygenation (ECMO)
- 3 Hospitalized, on non-invasive ventilation or high flow oxygen devices
- 4 Hospitalized, requiring supplemental oxygen
- 5 Hospitalized, not requiring supplemental oxygen - requiring ongoing medical care (COVID-19-related or other medical conditions preventing hospital discharge)
- 6 Hospitalized, not requiring supplemental oxygen - no longer requires ongoing medical care
- 7 Not hospitalized, limitation on activities and/or requiring home oxygen
- 8 Not hospitalized, no limitations on activities

